The RAI consists of seven 60-minute sessions scheduled over seven weeks as described in the *Intervention* section. During the first session, participants will receive an empty loose-leaf binder to store and organize completed self-assessments, reading materials, and homework assignments from each session. Participants will also receive a copy of the curriculum, *Getting Better and Better after Brain Injury: A Guide for Survivors, 2nd edition.*¹⁸³ They will be asked to review materials and complete worksheets between sessions. The RAI will be implemented by two experienced, licensed therapists ([name], [name]). Within each treatment condition, participants will be randomly assigned to one of the two therapists. Data will be analyzed to identify any therapist effects.

For the RAI+ participants, three booster sessions will be implemented as described in the

Intervention section of this proposal. The three weekly booster sessions will be scheduled to start

three months following completion of Session VII.

Implementation of quality control procedures: A protocol has been established to ensure the

quality and standardization of treatment implementation across therapists.

During the two-month project start-up period, the therapists ([name], [name]), and [name] will meet to review the manual and discuss implementation and standardization procedures. Following, each therapist will meet with volunteer participants, and implement Session I of the RAI curriculum. Informed written consent for digital audio-recording will be obtained. Afterward, the intervention audio-recordings will be reviewed with [name], with the manual in hand, to make certain that all steps are faithfully completed. Additionally, [name] will assure that therapists have covered the bolded content areas in the manual, which are considered to be key elements of treatment (see Appendix G). Strategies for improving consistency between therapists will be discussed and implemented. Changes will be made in the implementation manual (e.g., clarification of procedures) as needed.

The two therapists will meet again with the same volunteer participants, and implement the remaining six sessions of the RAI curriculum. Again, the audio-recordings will be reviewed with [name], and strategies for adherence to the manual will be discussed and implemented after each session.

Every six months thereafter, the complete quality control procedure will be reapplied.

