Additional quality control procedures will be implemented for booster sessions with each

therapist. As indicated in the Intervention section, booster sessions are person-centered and thereby

highly individualized. Audio-recordings will be made for the three booster sessions and reviewed

with [name] to ensure that key areas are covered as outlined in the manual. Every six months

thereafter, quality control procedures will be repeated.

Data collection procedures: Demographic, injury severity, and history information will be

collected at baseline using TBIMS standard procedures. For RAI and RAI+ participants, outcome

measures will be obtained prior to treatment (baseline) and following completion of the RAI.

Outcome measures for RAI+ participants will be obtained at the start and completion of the booster,

and six months following completion of the booster sessions. Measures for RAI participants will be

obtained at three, four, and nine months post-RAI treatment. Data collection will occur within the

same timeframe for both RAI and RAI+ participants as outlined in the figure that follows.

Project timeline: The major activities for the research project are sequentially delineated in the

Plan of Operation section.

E. Data Analysis

Descriptive statistics (e.g., means, standard deviations, proportions) will be calculated for all

measures at designated time intervals. Analyses will be performed using the university licensed

statistical program SAS v.9.3 (© 2002- 2010; SAS Institute Inc.; Cary, NC). The following table

provides a description of major statistical analysis procedures, emphasizing priority areas related to

research hypotheses. Information is provided regarding statistical hypotheses, statistical methods,

power analysis and sample size estimates. Analyses evaluating the RAI+ are based on the intent-to-

treat principle if drop-out is assumed as missing at random or missing completely at random.

Hypothesis 1 – Primary: Participants receiving the booster (RAI+ group) will report higher levels of resilience in comparison to individuals in the standard RAI group.

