Statistical Methods: A linear mixed-effects model will be used to model the CD-RISC scores over time for the RAI and RAI+ groups. The model will include fixed-effects for time at RAI+Booster initiation, conclusion, and long-term follow-up (e.g. 5, 6, and 11 months), group (RAI or RAI+) and the interaction between group and time. The model will also adjust for fixed-effects for injury severity, time postinjury, and education. Within-subject correlations in the CD-RISC scores over time will be modeled using a spatial power covariance pattern structure. Specific contrast statements will be used to test for a difference in the CD-RISC change scores between the treatment groups at both RAI+Booster initiation and conclusion as well as RAI+Booster initiation and long-term follow-up at a significance level of .05.

Power Analysis: Data obtained by our group indicated that the mean CD-RISC increased from a baseline value of 21.1 units to a mean of 28.4 units post-treatment (Difference=7.3), followed by a decline to 25.5 at the 3-month follow-up (Difference=2.9), with a standard deviation (SD) of the change score equal to 5.0. Considering a conservative SD of 6.0, this study will require 138 participants (n=69 per group) using a two-sample t-test performed at the 0.05 significance level to achieve 80% power. This effect translates to an effect size d=2.9/6.0=0.48, which is typically considered a moderate effect size.

Hypothesis 2: Participants in the RAI+ group will show better adjustment and lower levels of emotional distress as compared to persons in the standard RAI group.

Statistical Methods: Separate mixed-effects models, similar to that outlined in the methods for Hypothesis 1, will be used to model the responses for the MPAI-4 Adjustment Index and the BSI-18 GSI scores over time for each group. Specific contrast statements will be used to test the hypotheses of interest, each assuming a significance level of .05. Using a similar 40% decrease between the baseline to post-treatment values observed in our pilot study, we would expect the RAI+ to ameliorate declines in the MPAI-4 Adjustment and BSI-18 GSI scores by 1.7 and 2.6 points, respectively. Considering a conservative SD of 7.0, the 138 participants enrolled would provide power of 29% and 58% for the two outcomes, if analyzed by a two-sample t-test at the 0.05 level.

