Using randomization tables, participants will be assigned to either of two treatment groups: (1) Resilience and Adjustment Intervention (RAI), or (2) RAI+. After randomization, a second appointment will be scheduled. All participants will begin the 7-session treatment during their second appointment. The intervention consists of seven 60-minute sessions scheduled over seven weeks (see attached RAI Implementation Manual). During the first session, participants will receive an empty loose leaf binder to store and organize completed self-assessments, reading materials, and homework assignments from each session. They will be asked to review materials and complete worksheets between sessions. The intervention will be implemented by experienced, licensed therapists (Ph.D. level Interventionists). Participants will be randomly assigned to one of the therapists.

The RAI and RAI+ groups will both complete the post-treatment measures immediately after the seventh treatment session and then 3, 4, and 9 months later. Data collection at 3, 4, and 9 months post-treatment will be completed inperson, unless the participant requests to complete via phone.

Furthermore, the RAI+ group will complete 3 booster sessions, spaced approximately 7-10 days apart, beginning 3 months after completion of the seventh treatment session (booster sessions will occur between the 3 and 4 month data collection described above).

Data will be analyzed to identify any therapist effects, as well as treatment effects. For the RAI and RAI+ groups, demographic, injury severity, and history information will be collected at intake using standard procedures and protocols. All participants will complete the 4 outcome measures (Connor-Davidson Resilience Scale, CD-RISC; Mayo Portland Adaptability Inventory-4, MPAI-4; 13 Item Stress Test; and Brief Symptom Inventory-18, BSI-18) at 5 time points (intake, post-treatment, and 3, 4 and 9 month follow-up).

The RAI is not a standard of care at VCU. Both the RAI and the RAI+ are experimental interventions. Any information collected during the intervention sessions (e.g., questionnaires, lists generated) is part of the experimental intervention, not part of the research data.

7. * The IRB only reviews research activities, so indicate for each of the study activities described in the question above or in the protocol which activities are:

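### Does sizing the trial on a pilot loss that ends where the boosters begin undermine the 69 per group?

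*Combined protocol and SAP*

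**What the plan says.** In section E (Data Analysis), the Power Analysis under Hypothesis 1 describes the pilot RAI arm: a CD-RISC mean of 21.1 at baseline and 28.4 after treatment, "followed by a decline to 25.5 at the 3-month follow-up (Difference=2.9), with a standard deviation (SD) of the change score equal to 5.0". The calculation follows: "Considering a conservative SD of 6.0, this study will require 138 participants (n=69 per group", by a two-sample t-test at 0.05 with 80% power. "This effect translates to an effect size d=2.9/6.0=0.48".

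The Statistical Methods under the same hypothesis name what is compared: "difference in the CD-RISC change scores between the treatment groups at both RAI+Booster initiation and conclusion as well as RAI+Booster initiation and long-term follow-up". D6 (Procedure) schedules the boosters to start "three months following completion of Session VII", and the IRB form's Study Procedures agree: "beginning 3 months after completion of the seventh treatment session". The RAI group's later measures are "obtained at three, four, and nine months post-RAI treatment", so the two contrasts span about 1 and 6 months.

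Hypotheses 2 and 3 use differences of 1.7, 2.6, 1.6 and 0.9, obtained by applying a 40% fraction to the pilot gains, with stated power of 29%, 58%, 27% and 75%.

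The current justification, in the IRB form under Study Population, cites the primary-hypothesis power analyses for 69 per group and inflates for 28% attrition to 192. It repeats neither the difference nor the SD.

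**The concern.** The 2.9 points were lost between the end of the seven sessions and 3 months later. Over that period both arms of this trial receive the same treatment, so the same loss is expected in each and none of it enters either contrast. The contrasts start where the pilot loss ends. The pilot compared RAI with a wait list and stopped at 3 months, so it cannot estimate a booster effect or the SD of change after booster start.

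The SD raises a similar question. One value serves a contrast of about 1 month and another of about 6 months, although the spread of a change score normally grows with the interval.

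The figure of 69 per group underlies both the 154 in section E and the current 192. If its inputs were wrong for the contrasts being tested, the claimed 80% would mislead whoever reads a null result against it.

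**Working it through.** **1. The plan's own figures.** Inputs from section E, Hypothesis 1: difference 2.9, SD 6.0, 69 per group, alpha 0.05. Sidedness is not stated; two-sided reproduces the plan, while one-sided would need only 53 per group.

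- Noncentrality = (2.9/6.0) × √(69/2) = 0.483 × 5.874 = 2.84, on 136 degrees of freedom. Power = 80.5%.
- The smallest group size reaching 80% by the exact t calculation is 69, giving 138 in total.
- 138/0.90 = 153.3, rounded up to 154. 138/0.72 = 191.7, rounded up to 192.
- Secondary outcomes at 69 per group: 1.7/7.0 gives 29.4%, 2.6/7.0 gives 58.2%, 1.6/7.0 gives 26.6%, 0.9/2.0 gives 74.7%.

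All stated figures reproduce.

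**2. How the intervals line up.** Pilot loss: 28.4 − 25.5 = 2.9, from 0 to 3 months after the sessions. Contrasts: 3 to 4 months and 3 to 9 months after the sessions. They share only the 3-month point, so the observation about the source of 2.9 is correct.

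**3. What 2.9 means as an assumption.** The pilot gain was 28.4 − 21.1 = 7.3, and 2.9/7.3 = 39.7%. Used as a target, 2.9 says, for example, that boosters restore a loss of that size while RAI alone stays flat, or that RAI alone falls again by that much and boosters prevent it. Either is a coherent planning assumption.

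**4. Sensitivity at 69 per group, two-sided 0.05.**

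| Difference | SD | Power |
|---|---|---|
| 2.9 | 5.0 | 92% |
| 2.9 | 6.0 | 80% |
| 2.9 | 7.0 | 68% |
| 2.9 | 8.0 | 56% |
| 2.5 | 6.0 | 68% |
| 2.0 | 6.0 | 49% |
| 1.45 | 6.0 | 29% |

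The alternative values are illustrative. The documents do not favour any of them for the booster period.

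**5. One SD for two intervals.** The plan states: "Within-subject correlations in the CD-RISC scores over time will be modeled using a spatial power covariance pattern structure". Assume a constant visit SD *S*, no separate measurement-error term, and a 3-month change SD of 5.0. Then r(3) = 1 − 25/(2S²), r(t) = r(3)^(t/3), and SD of change = S√(2(1 − r(t))). The pilot RAI table gives *S* = 6.9 after treatment and 7.8 at 3 months.

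| S | r(3) | SD, 1 month | SD, 6 months | Power for 2.9, 1 month | Power for 2.9, 6 months |
|---|---|---|---|---|---|
| 6.9 | 0.737 | 3.03 | 6.59 | above 99% | 73% |
| 7.8 | 0.795 | 3.00 | 6.70 | above 99% | 71% |

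If 6.0 is taken as the 3-month SD instead, the 6-month SD is 7.64 to 7.83 and power is 60% to 58%, with power still above 99% at 1 month. Under these assumptions the planning SD of 6.0 is generous for the short contrast and somewhat low for the long one.

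**6. Secondary outcomes.** 0.40 × the pilot gains of 4.2, 6.6, 4.0 and 2.2 gives 1.68, 2.64, 1.60 and 0.88, which are the plan's inputs. From post-treatment to 3 months the pilot means for MPAI-4 Adjustment (51.2 to 50.7) and Ability (51.0 to 50.7) did not worsen. BSI-18 (57.2 to 58.7) and Stress (4.5 to 5.0) did. The 40% therefore appears to be carried over from CD-RISC. These outcomes do not set the sample size.

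**The case for a change.** The strongest case for a change is that disclosing where 2.9 came from is not the same as saying that it is carried to a different interval and a different comparison. A single 80% cannot describe contrasts of 1 and 6 months, and whether 6.0 is conservative depends on the interval. Someone reading only the IRB form sees 69 with no inputs at all.

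Part of this stands. The linking step is unstated, and the long contrast may well have less than 80% power for 2.9. The rest is weaker:

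- Section E gives both pilot means and the visit, so any reader can see that 2.9 is a loss over the first 3 months. It does not present the figure as an observed booster effect.
- The reason for sizing on lost gain is in the same document. The literature review and the Intervention section describe boosters as a means of holding and consolidating what the core sessions achieved.
- The sentence that reports 5.0 attaches it most naturally to the 2.9 change, and the plan then raises it to 6.0.
- The IRB form points to the primary-hypothesis power analyses. These stand in the grant proposal, which is in the same file and is listed among the approved uploads.
- For Hypotheses 2 and 3 the plan reports low power openly, so no reader is led to expect a firm answer there.

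**Conclusion.** The description of 2.9 is accurate, but nothing in the plan needs to change. The claim that 69 per group gives 80% power for a difference of 2.9 with SD 6.0 is true whatever suggested those values. Without a booster arm or data beyond 3 months, any value for the tested contrasts would also be an assumption, and the documents supply no better one. Relabelling 2.9 and 6.0 would leave the sample size, model, contrasts and conclusions as they are. When results are in, the confidence interval for each contrast will carry the information, and it uses the observed variance and not the planning SD.

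The residual uncertainty is about 71-73% power for the 6-month contrast and above 99% for the 1-month contrast. This holds if 5.0 is the SD of the 3-month change, visit SDs are constant, the spatial power structure holds without extra measurement error, and the true difference is 2.9 over both intervals. It shows that power may lie on either side of 80%, not that 138 evaluable participants or 192 enrolled is inadequate. This is a gap in exposition that a statistician reading section E can fill from the text.

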The proposed investigation differs from prior VCU research in several important ways. First, in response to recommendations made by research participants, Scientific Advisors, and Advisory Board members, the intervention period has been extended with three booster sessions. Boosters will be patient-focused and personalized to address the original RAI topics that were most relevant to the individual, as described in the *Intervention* section which follows. Furthermore, the project will thoroughly evaluate the sustainability of treatment gains by extending the follow-up period from three to nine months. The research design will compare the benefits of the original intervention (RAI) to an expanded, more person-centered intervention (RAI+).

B. Objectives

- 1. to evaluate the short and long-term efficacy of two structured outpatient intervention programs (RAI vs. RAI+) on resilience
- 2. to evaluate the short and long-term impact of intervention on emotional well-being and postinjury adjustment with the RAI vs. the RAI+
- 3. to evaluate the short and long-term impact of the RAI and the RAI+ on abilities including problem solving, communication, and stress management
- 4. to determine if demographic, lifestyle, injury, or treatment response information can predict maintenance of gains

C. Hypotheses

- 1. **Primary:** Participants receiving the booster (RAI+ group) will report higher levels of resilience in comparison to individuals in the standard RAI group.
- 2. Participants in the RAI+ group will show better adjustment and lower levels of emotional distress as compared to persons in the standard RAI group.
- 3. Additionally, participants in the RAI+ group will report greater abilities in the areas of problem solving, communication, and stress management relative to persons in the standard RAI group.
- 4. A participant's demographic, lifestyle, injury, and treatment response information will be predictive of maintenance ability.

D. Methodology

D1. Stage of Research

VCU's previous work with the RAI was best labeled as an "Intervention Development" project.

The present proposal is best labeled as falling within the "Intervention Efficacy" stage of research,

as the primary goal is to evaluate whether the RAI+ is feasible, practical, and has the potential to

yield sustainable and positive outcomes over and above the benefits of the RAI. The present

proposal also seeks to identify individual characteristics associated with positive outcomes. The

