A number of participants may be unavailable for follow-up. The accrual numbers presented in this proposal are based upon a review of data collection rates in past studies conducted at VCU. Furthermore, with more than 25 years of experience conducting follow-up studies, we have developed an effective follow-up system. The cornerstones of the system include: (a) providing high quality clinical follow-up services; (b) maintaining up-to-date contact information; and (c) employing an efficient appointment reminder system. Our system employs a combination of in-person, written, and telephone reminders. Most of our studies have included annual follow-ups, and follow-up rates have ranged between 90-95%.

Participants may be involved in concurrent individual psychotherapy or support groups or may be taking psychotropic medications. Individuals will be eligible for this study regardless of concurrent mental health treatment. As a matter of ethical practice, psychiatric consultation will be offered to individuals requesting services or who appear to be in need. Information about concurrent treatment will be obtained during each assessment session and recorded for each participant. Statistical analysis will be implemented to assess the relationship between concurrent therapy participation and treatment (RAI) outcome.

Interventions may not be completed within the proposed timeframe. Ideally, the RAI will be completed in seven weeks. For RAI+ participants, ideally booster sessions begin three months after completion of the RAI and will be completed in three weeks. Unforeseen delays may arise (e.g., related

to illness, transportation) that may affect timelines. We have built in windows that allow a modicum of flexibility. We will record completion dates and statistically evaluate how outcome data are affected by deviation from prescribed time intervals.

G. Expected Beneficial Impact

- An effective intervention for survivors will improve psychological outcomes and provide a means of counteracting the adverse, far-reaching effects of reduced inpatient lengths of stay.
- Use of effective patient-focused intervention and outcome tracking will provide an empirical foundation for utilizing person-centered interventions.
- All systems of care have resource limitations. Improved understanding of effective skill building, support, and education strategies will help systems more efficiently allocate resources.

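### One 80% power figure stands for two primary CD-RISC contrasts with different time gaps, and it is not shown to hold for the long-term one (month 5 to 11)

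*Combined protocol and SAP*

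**What the plan says.** In section III, E. Data Analysis, Hypothesis 1, the CD-RISC model has visits at about months 5, 6 and 11. The between-arm difference in change is tested "at both RAI+Booster initiation and conclusion as well as RAI+Booster initiation and long-term follow-up at a significance level of .05". The two gaps are therefore one month and six months. For the repeated measures, "Within-subject correlations in the CD-RISC scores over time will be modeled using a spatial power covariance pattern structure".

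The power paragraph first reports the pilot rise from 21.1 to 28.4 (7.3 points), then continues "followed by a decline to 25.5 at the 3-month follow-up (Difference=2.9), with a standard deviation (SD) of the change score equal to 5.0". It concludes "Considering a conservative SD of 6.0, this study will require 138 participants (n=69 per group" for 80% power with a two-sample t-test at 0.05. It names no contrast, gives no interval for the SD, and has no second calculation.

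The 2.9 points equal 2.9/7.3 = 40% of the pilot gain. Hypothesis 2 applies the same fraction to other outcomes: "Using a similar 40% decrease between the baseline to post-treatment values observed in our pilot study".

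Under D6. Procedure, the RAI-arm follow-up measures are "obtained at three, four, and nine months post-RAI treatment", in the same timeframe as the RAI+ arm. A. Rationale gives the purpose: "the project will thoroughly evaluate the sustainability of treatment gains by extending the follow-up period from three to nine months".

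The IRB application (Study Population, item 3) raises enrolment to 192 by allowing for 28% attrition and keeps 69 completers per group.

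**The concern.** The month 5-11 contrast is the sustainability test, the reason for extending follow-up. A reader would take 80% as its power, and would read a null long-term result as coming from an 80%-powered comparison.

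The plan's own covariance model makes correlation fall as visits move apart, so the SD of a six-month change exceeds that of a one-month change. A single difference of 2.9 and a single SD of 6.0 can match at most one of the two contrasts. The allowance from 5.0 to 6.0 is called conservative, but whether it is depends on the interval behind the 5.0, which is not given.

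The 2.9 is also a pilot decline from the end of treatment to three months, that is, before boosters would begin. The text does not label it as an assumed between-arm difference for either contrast.

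**Working it through.** **The plan's figure.** Two-sample t-test, two-sided 0.05, 69 per arm, difference 2.9, SD 6.0. Noncentrality = 2.9 / (6.0 × √(2/69)) = 2.84, giving power 80.5%. The stated size reproduces. The largest SD that still gives 80% at 69 per arm is 6.04.

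**Inputs for the check.** Visit SD σ: 6.9, 7.8 and 8.1, the RAI-arm CD-RISC SDs in the pilot results table. Difference 2.9 for both contrasts (assumed). Correlation over t months is ρ^t, as in a spatial power structure with constant variance (assumed to hold exactly).

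**Formulas.** If S is the SD of change over T months:
- ρ^T = 1 − S²/(2σ²)
- SD of change over t months = σ√(2(1 − ρ^t))
- SD at the later visit adjusted for the earlier score = σ√(1 − ρ^(2t))

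**Worked case: S = 5.0, T = 3, σ = 7.8.** ρ³ = 1 − 25/121.68 = 0.795, so ρ⁶ = 0.631. The six-month change SD is 7.8 × √(2 × 0.369) = 6.70, and power is 71.4%. The one-month change SD is 3.00, with power above 99%. The adjusted month-11 SD is 7.8 × √(1 − 0.631²) = 6.05, and power is 79.8%.

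**Month 5-11 at 69 per arm, by reading of the SD (ranges over σ):**

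| Reading | SD, raw change | Power, raw change | SD, adjusted | Power, adjusted |
|---|---|---|---|---|
| 5.0 over 3 months (post-treatment to follow-up) | 6.59-6.73 | 71-73% | 5.79-6.12 | 79-83% |
| 5.0 over 7 weeks (baseline to post-treatment) | 8.04-8.46 | 52-56% | 6.53-7.21 | 65-74% |
| 5.0 over about 4.6 months (baseline to 3-month follow-up) | 5.58-5.62 | 85-86% | 5.11-5.27 | 89-91% |
| 6.0 is itself the 6-month SD | 6.00 | 80.5% | 5.40-5.57 | 86-88% |

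**Why adjustment helps in every row.** With equal visit variances and correlation r between months 5 and 11, adjusted SD / change SD = √((1 − r²)/(2(1 − r))) = √((1 + r)/2). This is below 1 whenever r < 1.

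**Effect of enrolling 192 (96 per arm).** At 28% attrition, 96 × 0.72 = 69 per arm and the table applies. F. Feasibility says "follow-up rates have ranged between 90-95" percent in most past studies. That leaves 96 × 0.90 = 86 to 96 × 0.95 = 91 per arm, and the 3-month reading then gives 80-84% for the raw change contrast.

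**Difference needed.** On the 3-month reading at 69 per arm, 80% power for month 5-11 needs about 3.2 points instead of 2.9.

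**The case against.** A reader might infer that the long-term test is underpowered at 71-73%, because the 5.0 follows directly after the 3-month decline. The documents do not support that as a finding. The sentence reports two changes, 7.3 and then 2.9, before it mentions the change-score SD, and word order alone does not settle the interval.

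The pilot confidence interval for the post-treatment difference (4.96 to 8.43) does not settle it either. It implies a standard error of 3.47/3.92 = 0.885. If about 64 per arm were analysed (an assumption, since the analysed number is not given), the SD is 0.885 × √(64/2) = 5.0, which fits a 7-week SD at least as well. That reading lowers power, while the baseline-to-follow-up reading raises it above 80%.

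Three further objections stand:
- Spatial power is a modelling choice, not evidence of how CD-RISC scores decay. If 30-60% of visit variance were stable between persons (assumed) and 5.0 is a 3-month SD, the six-month SD is 5.8-6.6 and power 73-83%.
- The difference at month 11 is unknown and could be larger or smaller than 2.9.
- 28% is described as a maximum attrition, and at past follow-up rates the 3-month reading reaches 80%.

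Change from booster initiation is also a legitimate specification, so the contrast is not an error. What none of this answers is that one figure is offered for two contrasts, with the SD's interval unstated.

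**Conclusion.** The point holds as a gap in the power justification. The arithmetic is correct, but under the plan's own covariance one difference and one SD cannot give 80% for both primary contrasts, and the plan does not show 80% for month 5-11. That much needs no assumption about the 5.0.

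The size does need assumptions. With 2.9 points, 69 completers per arm, exact spatial-power decay and a visit SD of 6.9-8.1, the readings above run from 52% to 86%. A shortfall is possible and not established. On all of these readings month 5-6 has power above 98% for the same 2.9 points, so the uncertainty falls on the long-term contrast.

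It should be fixed before analysis. The design and the enrolment target stand.

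**What to change.** 1. Replace the two raw change contrasts with between-arm comparisons at month 6 and month 11, adjusted for the booster-initiation CD-RISC score. Both arms already provide that score before their treatment differs. Specify this before analysis, with a stated rule for a participant whose initiation score is missing. The table shows the gain for month 5-11 at the same N.
2. From the pilot data, state the interval over which the 5.0 was measured. Label 2.9 as an assumed difference for each contrast. Replace the single 80% with a power for each contrast, using an SD for its own interval. The sponsor should compute these. Neither 71-73% nor any other range inferred here should be printed as the plan's figure.
3. State which of the two contrasts is primary.

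Cost: enrolment, visits and measures are unchanged and no new data are needed. The power paragraph is reworded and the primary contrasts are re-specified. If the sponsor keeps the raw change contrasts, items 2 and 3 still apply, and the stated long-term power may turn out lower than 80%.
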